6. DATA CONVENTIONS

The following analysis conventions will be used in the statistical analysis.

6.1. Definition of Baseline for Efficacy/Safety Variables

Unless otherwise specified, the Baseline assessment for all measurements will be the latest available valid measurement taken prior to the administration of investigational product. The following rules specify the determination of baseline by both date/time information:

- The date and time of first injection will be used to determine the baseline for the AE, lab, PK and ADA data.
- Only the date of first injection will be used to determine the baseline for other data except the AE, lab, PK and ADA data.

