#### **Definition of baseline**

The last assessment before the administration of study drug on day 1 will be considered as the baseline evaluation.

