4.6.4. Vital Signs and Weight/Height

Vital signs include systolic and diastolic blood pressure, respiratory rate and heart rate. Vital signs will be collected in a seated position. On the day of study drug administration, vital signs are taken

CONFIDENTIAL

Page 29 of 35

prior to PK blood draw, prior to study drug administration, and at 2 hours (± 10 min) after completion of the injection.

Weight and height are measured at screening visit 1 only.

4.6.5. 12-Lead Electrocardiography (ECG)

A standard 12-lead ECG will be performed at the screening visit 1 only. Heart rate will be recorded from the ventricular rate and the PR, QRS, and QT intervals will be recorded. The ECG strips or reports will be retained with the source documentation.

To minimize variability, it is important that the patient be in a resting position for ≥ 10 minutes prior to the ECG evaluation. Body position should be consistently maintained for each ECG to prevent changes in heart rate.

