* Study days are calculated from the day of 1st injection. Study day = (date of assessment -1^{st} injection date +1) when date of assessment ≥ 1 st injection date; otherwise study day = (date of assessment -1^{st} injection date). If subject never received any dose of study drug, randomization date will be used in the place of 1st injection date. # Post-baseline urinalysis will not be mapping since no scheduled measurements will be collected per protocol.

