- 6. TNSS, TOSS, and DMS will be recorded daily via e-diary, starting at the randomization visit until EOS. Refer to Protocol Section 9.2.4.1, 9.4.2.2 and 9.4.2.4 for procedural details.
- 7. In asthmatic subjects, ACQ-5 scores will be recorded weekly via e-diary, starting from the randomization visit until EOS. Refer to Protocol Section 9.2.4.6 for procedural details.
- 8. In all subjects, RQLQ (S) scores will be recorded weekly via e-diary starting from the randomization visit until EOS. Refer to Protocol Section 9.2.4.7 for procedural details. In asthmatic subjects, the weekly RQLQ (S) and ACQ-5 assessments may be performed on the same day.
- 9. Refer to for Protocol Section 9.2.4.8 procedural details.
- 10. Refer to for Protocol Section 9.2.4.9 procedural details.
- 11. Vital signs include systolic and diastolic blood pressure, respiratory rate and heart rate. Vital signs will be collected in a seated position. At the randomization visit, vital signs are taken prior to PK blood draw, prior to study drug administration, and at 2 hours (±10 min) after completion of the injection.
- 12. A full physical exam must be performed at screening, at baseline, and at EOS. A limited physical exam will be done at remaining visits depending on presentation of the subject.
- 13. If the urine pregnancy test is positive, the site must perform a serum pregnancy test for confirmation. At the randomization visit, if a serum pregnancy test must be performed,

CONFIDENTIAL

Page 52 of 56

VV-RIM-00163457-1.0 Approved - 04 Aug 2021 GMT-5:00

study drug cannot be administered unless the serum pregnancy test is negative. Urine pregnancy test can be performed on day -1 of the visit at the investigator's discretion.

At-home pregnancy testing: WOCBP will be provided with urine pregnancy tests for at-home testing prior to visits 4 and 6. Study sites will collect the results by telephone at these visits. If the urine pregnancy test is positive, the site must perform a serum pregnancy test for confirmation.

- 14. PK and ADA samples are to be collected prior to study drug administration. In the event of suspected SAEs, such as anaphylaxis or hypersensitivity, additional samples for PK and ADA analyses may be collected as close to the event as practically possible.
- 15. Refer to Protocol Section 9.2.11.

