RBC	<4 Tera/L and ≥ 4 Tera/L at baseline for Male; <3 Tera/L and ≥ 3 Tera/L at baseline for Female ≥ 7 Tera/L and <7 Tera/L at baseline for Male; ≥ 6 Tera/L and <6 Tera/L at baseline for Female	Unless specifically required for particular drug development, the analysis is redundant with that of Hb.
Platelets	<100 Giga/L and ≥100 Giga/L at baseline ≥700 Giga/L and < 700 Giga/L at baseline	International Consensus meeting on drug-induced blood cytopenias, 1991. Two independent criteria
Vital signs		
HR	\leq 50 bpm and decrease from baseline \geq 20 bpm \geq 120 bpm and increase from	
SBP	≤95 mmHg and decrease from baseline ≥20mmHg ≥160 mmHg and increase from baseline ≥20 mmHg	
DBP	≤45 mmHg and decrease from baseline ≥10 mmHg ≥110 mmHg and increase from baseline ≥10 mmHg	
Respiratory rate	< 12 per minutes and ≥12 per minute at baseline >20 per minute and ≤20 per minute at baseline	

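### The date-only baseline rule in SAP 6.1 cannot separate the pre-dose vital signs from the 2-hour post-dose reading on day 1, and so permits a post-dose baseline

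*SAP*

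**What the plan says.** **Baseline rules.** SAP 6.1 opens with a general rule: "the Baseline assessment for all measurements will be the latest available valid measurement taken prior to the administration of investigational product". Two bullets then say how baseline is determined. The first: "The date and time of first injection will be used to determine the baseline for the AE, lab, PK and ADA data". The second: "Only the date of first injection will be used to determine the baseline for other data except the AE, lab, PK and ADA data". Vital signs are not named in either bullet, so they belong to the second. Protocol 11.5 has one rule for all data: "The last assessment before the administration of study drug on day 1 will be considered as the baseline evaluation". SAP 1.2.3, which lists departures from the protocol's statistical section, mentions no change to the baseline definition.

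**Timing of readings.** On the dosing day, according to the footnotes to the SAP 10.2 schedule, "vital signs are taken prior to PK blood draw, prior to study drug administration, and at 2 hours (±10 min) after" the injection is complete. SAP 4.6.4 and protocol 9.2.5.1 give the same timing. The remaining scheduled readings are at screening and at Visit 5; none is scheduled at the end-of-study visit.

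**Use of baseline.** SAP 5.7.3 summarises vital signs and their change from baseline by visit, and counts treatment-emergent PCSVs. Protocol 11.4.5.2 asks for change to each scheduled assessment time. The vital-sign PCSV criteria in SAP 10.3 refer to baseline; the one for low systolic pressure is "≤95 mmHg and decrease from baseline ≥20mmHg".

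**The concern.** Vital signs are the one measurement that the schedule explicitly places on both sides of the injection on day 1. PK and ADA samples on that day are drawn before dosing, and haematology and chemistry have no scheduled post-dose draw. Time of day is therefore used where the schedule needs it least and left out where it is needed to tell a baseline value from a post-dose one.

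Only two vital-sign readings are scheduled after dosing: the 2-hour reading and Visit 5. Protocol 3.3 regards reactions arising at once or within hours of administration as the most concerning form of hypersensitivity, and hypersensitivity incidence is part of a secondary objective. If the 2-hour value is taken as baseline, half of the scheduled post-dose vital-sign data is lost as post-baseline information, and the other half is compared with the wrong reference.

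**Working it through.** The plan gives no figure to reproduce here. The check sets the rules side by side and applies them to one hypothetical subject.

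**Step 1: which rule covers vital signs.** The date-and-time bullet names four data types, and vital signs are not among them. The date-only bullet covers the rest.

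**Step 2: what date alone can do.** The pre-dose and 2-hour readings share one calendar date. The bullet does not say whether an eligible date must be on or before the injection date, or strictly before it. On or before, taking the latest value, gives the 2-hour reading. Strictly before gives the screening reading, nominally 7 to 84 days earlier, and discards the day-1 pre-dose value. Neither gives the last pre-dose value.

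**Step 3: the analysis windows.** SAP 6.4 states: "Study days are calculated from the day of 1st injection". Study day is the date difference plus 1, so the 2-hour reading has study day 0 + 1 = 1. The vital-sign windows are Baseline ≤1 and Visit 5 ≥2. The 2-hour reading falls in the baseline window, and no window exists for a post-dose reading on day 1. This fits the on-or-before reading. However, the windows formally apply only when scheduled-visit data are unavailable, so they support that reading without settling it.

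**Step 4: worked example.** All values are assumed systolic pressures in mmHg: screening 122, day-1 pre-dose 120, day-1 at 2 hours 92, Visit 5 120. The low-systolic PCSV needs a value of at most 95 and a fall of at least 20.

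| Reading of the rule | Baseline | Change at 2 h | PCSV at 2 h | Change at Visit 5 |
|---|---|---|---|---|
| Last pre-dose value (SAP 6.1 opening sentence, protocol 11.5) | 120 | 92 − 120 = −28 | Yes | 120 − 120 = 0 |
| Date on or before injection, latest value | 92 | 92 − 92 = 0 | No | 120 − 92 = +28 |
| Date strictly before injection | 122 | 92 − 122 = −30 | Yes | 120 − 122 = −2 |

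The second row loses the acute fall and reports a spurious rise of 28 mmHg at Visit 5. The third row keeps the acute fall but measures it from the wrong reading.

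**Step 5: the 2-hour time point.** Whichever baseline is used, SAP 5.7.3 reports by visit, and neither it nor SAP 6.4 names a 2-hour post-dose time point. Protocol 11.4.5.2 covers every scheduled assessment time, which includes that reading.

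**The case against.** The strongest reply is that SAP 6.1 already requires a pre-dose value in its opening sentence. The bullets only put that sentence into operation, and a reading labelled as 2 hours after injection cannot be a pre-dose one. A careful programmer would use the time-point label and obtain the value that protocol 11.5 wants. This carries weight, and it means that a post-dose baseline is not a settled outcome. It does not remove the conflict. The opening sentence allows for exceptions specified elsewhere, the bullets are presented as the operative rules, and both literal date-only readings contradict the sentence above them.

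A reader might go further and infer that the 2-hour reading will be the baseline and that acute changes will vanish from the safety tables. The documents do not support that, for four reasons:

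- Only one of the three readings gives that result.
- The SAP 6.4 windows are a fallback for missing scheduled data, and both day-1 readings are scheduled.
- SAP 5.7 counts abnormalities from the first injection, so with a pre-dose baseline the 2-hour value is eligible as a treatment-emergent PCSV.
- Injection reactions must be reported as AEs (protocol 8.4.1). Abnormal vital signs are AEs when symptomatic, treated or judged so by the investigator (protocol 10.1.1). Systemic or severe hypersensitivity has its own AESI table (SAP 5.7.1 and 10.4).

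A clinically important reaction would therefore still be visible in the AE output. The exposure is limited to the numeric vital-sign summaries.

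**Conclusion.** The point holds as a defect in a stated rule. For vital signs, the date-only bullet in SAP 6.1 conflicts with that section's opening sentence and with protocol 11.5. Applied literally, it permits a post-dose baseline or falls back to screening. The harm arises mainly in the first case, and is confined to the vital-sign change-from-baseline and PCSV tables. The missing 2-hour time point is a second gap that exists under any reading of the baseline rule.

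On size: every treated subject is scheduled for a 2-hour reading, so up to about 300 baselines could be affected. That is not a count of subjects whose PCSV status would change. The documents give no basis for such a count, and the example rests on assumed pressures. The primary endpoint, an in-season average, uses no vital-sign baseline and is untouched. The correction should be made before database lock, because the choice would otherwise be left to programming.

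**What to change.** In SAP 6.1, move vital signs to the date-and-time rule so that baseline is the last pre-dose reading. The documents specify when vital signs are taken but do not show that clock times are recorded. If they are not, select baseline by the pre-dose or post-dose time-point label instead.

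In SAP 5.7.3 and in the SAP 6.4 vital-sign windows, list day 1, 2 hours post-dose as a post-baseline time point, and include it in the change-from-baseline and PCSV summaries.

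The cost is a few lines of SAP text, one added row in the window table and the matching programming specification. No trial procedure changes, and the SAP is brought back into agreement with protocol 11.5 and 11.4.5.2.

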6.2. Data Handling Conventions

For the laboratory safety variables and biomarker data, if the data are below the lower limit of quantification (LLOQ)/limit of linearity, half the lower limit value (i.e., LLOQ/2) will be used for quantitative analyses. For data above the upper limit of quantification (ULOQ)/ limit of linearity, the upper limit value (i.e., ULOQ) will be used for quantitative analyses

6.3. Data Handling Convention for Missing Data

Missing data will not be imputed in listings. This section includes the methods for missing data imputation for some summary analyses, if necessary.

Rules for handling missing data for primary and secondary efficacy variables are described in Section 4.5.1 and Section 4.5.2.

Adverse event

If the intensity of a TEAE is missing, it will be classified as "severe" in the frequency tables by intensity of TEAEs. If the assessment of relationship of a TEAE to the investigational product is missing, it will be classified as related to the investigational product.

Adverse event start date

AE start date will be used for AE classification and analysis of AESIs. If AE start date is not complete, then the character variable will keep the original incomplete date, the numerical date variable will be imputed, and an imputation flag will be used to indicate which date component is missing.

If AE start day is missing, and AE start month and year are not missing: If AE start year is the same as first dose year and AE start month is the same as first dose month, then AE start day will be imputed using the day of first dose. If this leads to a date after the AE end date, AE end date will be used instead. If AE start year is the same as first dose year and AE start month different from first dose month, AE start day will be imputed using the first day of the month. If this leads to a date before informed consent date, the informed consent date will be used. Imputation flag is 'D'.

Regeneron Pharmaceuticals, Inc. Statistical Analysis Plan

If AE start month is missing, and AE start year is not missing: If AE start year is before the first dose year, the informed consent day and month will be used. If AE start year is the same as first dose year, the first dose day and month will be used. If this leads to a date after AE end date, AE end date will be used instead. If AE start year is after the first dose year, January 1st will be used. Imputation flag is 'M'.

If AE start year is missing: The date of first dose will be used. If this leads to a date after the AE end date, AE end date will be used instead. Imputation flag is 'Y'.

Adverse event end date

The general recommendation is not to impute AE end date. However, since AE end date will be used for AE start date imputation, to carry through the logic for programming, the following intermediate step will be used. Afterwards, only the original character/numeric date recorded in CRF will be kept in the final analysis dataset.

If AE end day is missing, and AE end month and year are not missing: AE end date will be imputed using the last day of the month. If this leads to a date after end of study follow up date, the end of follow up date will be used instead.

If AE end month is missing, and AE end year is not missing: AE end date will be imputed using December 31st as the day and month. If this leads to a date after end of study follow up date, the end of follow up date will be used instead.

If AE end year is missing: AE end date will be imputed using end of follow up date.

Prior or concomitant medication

Medication start and end date missing

To determine whether a medication is prior medication or concomitant medication or both, the missing medication start date is estimated as early as possible, and the missing medication end date is estimated as late as possible. If the medication start date is missing, the onset day will not be calculated in medication listing.

Prior medication start date

If start day is missing, and start month and year are not missing: the start day will be imputed using the first day of the month. Imputation flag is 'D'.

If start month is missing, and start year is not missing: the day and month will be imputed using January 1st. Imputation flag is 'M'.

If start year is missing: the start date will be imputed using 2 years before informed consent date. Imputation flag is 'Y'.

A special note: for start date with year missing, the general principle is not to impute. However, to simplify the programming flow, the imputation is proposed to align with protocol which specifices to collect up to 2 years prior medication. Since the start date of prior medication will not be used in any analysis, the rule will not impact the analysis result.

Prior medication end date

If end day is missing, and end month and year are not missing: the end date will be imputed using the last day of the month. If this leads to a date on or after first dose intake date, the first dose intake date -1 will be used. Imputation flag is 'D'.

If end month is missing, and end year is not missing: the end date will be imputed using December 31st as the day and month. If this leads to a date on or after first dose intake date, the first dose intake date -1 will be used instead. Imputation flag is 'M'.

If end year is missing: the end date will be imputed using the first dose intake date -1. Imputation flag is 'Y'.

Concomitant medication start date

The imputation rule for concomitant medication start date is the same as AE start date.

Concomitant medication end date

If end day is missing, and end month and year are not missing: the end date will be imputed using the last day of the month. If this leads to a date after end of study follow up date, the end of follow up date will be used. Imputation flag is 'D'.

If end month is missing, and end year is not missing: the end date will be imputed using December 31st as the day and month. If this leads to a date after end of study follow up date, the end of follow up date will be used instead. Imputation flag is 'M'.

If end year is missing: the end date will be imputed using the end of follow up date. Imputation flag is 'Y'.

Medication coding

Medications whose ATC level 4 cannot be coded will be summarized by setting ATC4=ATC2 in the table programs. However, these uncoded ATC level 4 records still need to be confirmed with study data manager and study medical director.

PCSV

Subjects who had post-baseline PCSV but missing baseline value will be regarded as having treatment-emergent PCSV

6.4. Analysis Visit Windows

Data analyzed by-visit-analysis (efficacy [excluding daily diary data], laboratory data, vital sign) will be summarized by the study scheduled visits described in the study protocol and SAP "Schedule of Event".

The analysis visit windows are created per study Schedule of Events (SOE) table for each parameter and will be applied if the data from study scheduled visits are unavailable. The following general rules will be applied to unscheduled visit and/or early termination (ET) visit mapping for each parameter.

1. If ET visit falls in an analysis window which already has non-missing observed value of this parameter from the scheduled visit, ET will be mapped to the next scheduled visit.

CONFIDENTIAL

Page 39 of 56

- 2. If both ET visit and unscheduled visit of the same parameter are available in the same analysis visit window, only ET visit will be mapped.
- 3. If multiple unscheduled visits of the same parameter are available in the same analysis visit window, the unscheduled visis will be mapped using the following rules:
 - a. The closest unscheduled visit from the target day will be selected
 - b. If multiple unscheduled visits exist on the same day, the first unscheduled visit will be used.
- 4. If mapping distance is greater than 4 weeks, the unscheduled visit will not be mapped.

Unscheduled visits and early termination (ET) visit will be mapped per the following analysis visit windows based on the study day/visit of each parameter.

Visit from SOE	Target Study Day*	PFASQ, SPT	PGI-S
Baseline	1	≤1	≤ 1
Visit 5	57		[2, 85]
Visit 7 (EOS)	113	≥ 2	≥ 86

Analysis Visit Window for Efficacy Endpoints

*Study days are calculated from the day of 1^{st} injection. Study day = (date of assessment -1^{st} injection date +1) when date of assessment $\ge 1^{st}$ injection date; otherwise study day = (date of assessment -1^{st} injection date). If subject never received any dose of study drug, randomization date will be used in the place of 1^{st} injection date.

Visit from SOE	Target Study Day*	Vital Sign	Physical Exam	Laboratory#, PK	ADA	Serum total IgE, Serum sIgE for birch pollen and Bet v 1 and other regional or relevant allergens, Serum sIgE for concomitant and homologous allergens
Baseline	1	≤ 1	≤ 1	≤ 1	≤ 1	≤ 1
Visit 5	57	≥2		[2, 85]		[2, 85]
Visit 7 (EOS)	113		≥2	≥86	≥2	≥86

Analysis Visit Window for Safety and Biomarkers

* Study days are calculated from the day of 1st injection. Study day = (date of assessment -1^{st} injection date +1) when date of assessment ≥ 1 st injection date; otherwise study day = (date of assessment -1^{st} injection date). If subject never received any dose of study drug, randomization date will be used in the place of 1st injection date. # Post-baseline urinalysis will not be mapping since no scheduled measurements will be collected per protocol.

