# 3.2. Rationale

## 3.2.1. Rationale for Study Design

### Study design and duration

This is a phase 3 multi-center, randomized, double-blind, placebo-controlled, parallel group study to assess the efficacy of anti-Bet v 1 mAbs (REGN5713-5714-5715) to reduce allergic rhinitis and conjunctivitis during birch pollen season. The study will last approximately 28 weeks, including screening (refer to Table 1 for a schedule of events). The actual duration of the study will vary depending on the start, peak, and end dates of the local birch pollen season for each study site, which will be variable across different geographies (refer to Section 9.2.2):

- Screening: Generally healthy male and female subjects 18 years and older with a history of birch allergy for at least 2 years will undergo screening visits before the onset of the birch pollen season. Subjects will be asked to refrain from taking specific prohibited medications within the specified period preceding screening (refer to Section 8.9.1).
- **Randomization**: Candidate subjects who meet all inclusion and no exclusion criteria will be randomized and receive the study drug. Randomization will be stratified based on geographical regions and sIgE levels at screening (refer to Section 8.5).
- **In-season visits**: Approximately 1 month after randomization (timing will vary based on the local pollen season), a telephone contact will occur to collect any AEs and concomitant medication information. There will be an in-clinic visit at the anticipated local peak of birch pollen season. An additional telephone contact will occur at the end of the local birch pollen season. An in-clinic visit will occur at the end of the study. Subjects will be asked to stop using specific rescue medications within 5 days of the end of study visit (refer to Section 8.9.1).

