#### 9.1.1. Footnotes for the Schedule of Events Table

- Screening SPT for birch, birch homologous trees, and other common allergens will be performed as described in the study manual. Skin prick test for birch should be performed prior to other screening assessments. If screening SPT for birch is negative (ie, mean wheal diameter <5 mm greater than a negative control), then other screening visit procedures do not need to be performed as the subject will have failed screening (refer to Section 7.2.1 Inclusion Criteria, #3).
- 2. Randomization may occur within 1 day prior to study drug administration. All safety assessments performed at screening must be normal and checked against the inclusion/exclusion criteria prior to study drug administration.
- 3. The timing of in-clinic visits may vary for each study site, depending on the start, peak, and end dates of the local birch pollen season (as determined by local pollen counts; refer to Section 9.2.2). The randomization visit will be scheduled approximately 2 weeks before the start of birch pollen season, and the end of study (EOS) visit approximately 16 weeks after the randomization visit (depending on the duration of the local birch pollen season). In addition, visit 5 will be scheduled to occur within 2 weeks of the anticipated local peak of the birch pollen season.
- 4. If randomization occurs >60 days after the screening visit, medical history, blood chemistry, hematology, and spirometry must be repeated prior to randomization.
- 5. E-diary and rescue medications will be dispensed at the randomization visit. E-diary and any unused rescue medications will be returned at the EOS visit. Refer to Section 8.2 for more information on rescue treatments.
- 6. TNSS, TOSS, and DMS will be recorded daily via e-diary, starting at the randomization visit until EOS. Refer to Section 9.2.4.1, Section 9.2.4.2, and Section 9.2.4.4 for procedural details.
- 7. In asthmatic subjects, ACQ-5 scores will be recorded weekly via e-diary, starting from the randomization visit until EOS. Refer to Section 9.2.4.6 for procedural details.
- 8. In all subjects, RQLQ (S) scores will be recorded weekly via e-diary starting from the randomization visit until EOS. Refer to Section 9.2.4.7 for procedural details. In asthmatic subjects, the weekly RQLQ (S) and ACQ-5 assessments may be performed on the same day.
- 9. Refer to for Section 9.2.4.8 procedural details.
- 10. Refer to for Section 9.2.4.9 procedural details.

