## 9.1.2. Early Termination Visit

Subjects who are withdrawn from the study after randomization or at any time before the end of study visit will be asked to return to the study site for an early termination (ET) visit. Refer to Table 1 for assessments to be performed at an ET visit.

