2.3. Sample Size and Power Considerations

This study is powered to detect differences between REGN5713-5714-5715 and placebo on the primary endpoint of the average CSMS during birch pollen season. A sample size of 120 subjects per arm gives 90% power to detect a mean difference in average CSMS of 1.9 (30% reduction from placebo) in REGN5713-5714-5715 (mean CSMS = 4.4) and placebo (mean CSMS = 6.3),

assuming a common standard deviation in CSMS of 4.5 with a two-sample t-test at 2-sided significance level of 0.05. Assuming 20% drop out rate during the birch pollen season, the target is to randomize 150 subjects per arm.

Estimates of mean and variability of the CSMS are based on pooled estimates across several field studies for grass sublingual immunotherapy, and a 30% treatment effect relative to placebo is in line with what was observed in the phase 1b POC study for REGN5713-5714-5715.

This planned sample size (150 subjects per arm) also gives 93% power to detect a mean difference in TNSS of 0.6 (26% reduction from placebo) in REGN5713-5714-5715 (mean TNSS=1.7) and placebo (mean TNSS=2.3), assuming a common standard deviation in TNSS of 1.5 at 2-sided alpha of 0.05 using a two-sample t-test. The assumptions of TNSS endpoint are based on effects observed in the GT-08 trial of timothy grass sublingual tablet (Dahl, 2006). With the same mean for placebo and common standard deviation from GT-08 but a 30% reduction from placebo for REGN5713-5714-5715 as observed in the phase 1b POC study, the study will have a greater power.

The sample size and power calculations were performed using nQuery Advisor 7.0

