5.8. Analysis of Pharmacokinetic Data

Descriptive statistics of total REGN51713, total REGN5714, total REGN5715, and total drug (REGN5713+REGN5714+REGN5715) concentrations in serum at each sampling timepoint will be provided. Plots of mean concentration versus nominal time will be presented. Select PK parameters may be calculated.

Exposure-response analysis for biomarkers, efficacy, and safety endpoints may be conducted as appropriate, and presented in separate reports.

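### SAP 6.4 reports an early-termination PK sample drawn by day 85 as Visit 7 (day 113) when Visit 5 is filled, which probably overstates the late concentration mean

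*SAP*

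**What the plan says.** SAP 6.4 sets rules for placing unscheduled and ET visits into analysis windows, parameter by parameter.

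- **Rule 1:** if the ET visit lands in a window that already has an observed value "from the scheduled visit, ET will be mapped to the next scheduled visit".
- **Rule 4:** "If mapping distance is greater than 4 weeks, the unscheduled visit will not be mapped". It does not mention ET visits.
- **Windows:** PK shares the column headed "Laboratory#, PK". Visit 5 (target day 57) takes days 2 to 85, and Visit 7 (target day 113) takes day 86 onward.

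The schedule of events (Protocol Table 1, SAP Table 3) has only two scheduled post-dose PK visits, Visit 5 and EOS/ET Visit 7. Visit 6 is a telephone contact with no sampling. Subjects who withdraw "will be asked to return to the study site for an early termination (ET) visit", and PK is marked in that column.

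SAP 5.8 summarises concentrations at each sampling timepoint and adds: "Plots of mean concentration versus nominal time will be presented". SAP 4.7 lists both nominal and actual time as PK variables, but SAP 5.8 commits to no actual-time display. Total concentration in serum over the study is a secondary endpoint (Protocol 4.2).

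**The concern.** A subject who gives a Visit 5 sample and withdraws by day 85 has an ET sample in a window that is already occupied. Rule 1 moves it to the next visit with PK, which is Visit 7. It then enters a day-113 mean although it was drawn 28 or more days before day 113. The plan treats a distance above 4 weeks as too far for an unscheduled visit, but as worded it sets no such limit for ET.

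After a single dose, an earlier sample in the declining phase is higher than a later one from the same subject. Visit 7 is the only late PK point in the trial, so a summary that mixes day-60 to day-85 samples into it tends to make late exposure look better than it was. What is at stake is the accuracy of a descriptive secondary endpoint at its last timepoint.

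**Working it through.** **1. The plan's own figure.** SAP 2.3 gives 120 evaluable subjects per arm for 90% power (difference 1.9, SD 4.5, two-sided 0.05). Recomputing, 118 per arm are needed, and power at 120 is 0.905 (0.903 by noncentral t). Then 120 / 0.80 = 150, matching "Assuming 20% drop out rate during the birch pollen season, the target is to randomize 150 subjects per arm". The allowance is therefore up to 30 leavers in the active arm. It is a sample-size allowance, not a forecast.

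**2. Displacement.** Distance = 113 − ET day. Day 85 gives 28 days, day 71 gives 42, and day 58 gives 55. Every moved sample is at least 28 days from target. Had rule 4 covered ET visits, only day 85 exactly would pass, since 28 is not greater than 28.

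**3. Effect on one subject.** Assume first-order decline. Ratio to the subject's own day-113 level = 2^((113 − d)/h). No half-life h is documented, so 21 and 28 days are assumed.

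- Day 85: 2^(28/28) = 2.00 and 2^(28/21) = 2.52.
- Day 71: 2^(42/28) = 2.83 and 2^(42/21) = 4.00.
- Outside that range, a day-85 sample gives 2^(28/14) = 4.00 at 14 days and 2^(28/42) = 1.59 at 42 days.

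**4. Illustrative effect on the Visit 7 mean.** Assumptions, none documented as fact:

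- Dropout is spread evenly over days 15 to 85. Day 15 follows from "The randomization visit will be scheduled approximately 2 weeks before the start of birch pollen season". Day 85 is the nominal day of Visit 6, the call described by "An additional telephone contact will occur at the end of the local birch pollen season".
- Visit 5 falls on day 57, there is no dropout after day 85, and all subjects share one curve.
- 25%, 50% or 100% of those leaving after Visit 5 give an ET sample.

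The share leaving after day 57 is 28/70 = 40%. Averaged over days 57 to 85, the ratio r is 2.89 (h = 28) or 4.14 (h = 21). With N completers and m moved samples, the mean is inflated by (N + m·r)/(N + m).

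| Dropout | N | m | h = 28 | h = 21 |
|---|---|---|---|---|
| 20% (30 of 150) | 120 | 3, 6, 12 | 5%, 9%, 17% | 8%, 15%, 29% |
| 5% (7.5 of 150) | 142.5 | 0.75, 1.5, 3 | 1%, 2%, 4% | 2%, 3%, 7% |

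Example: (120 + 6 × 2.89)/126 = 1.09.

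**5. Is the direction certain?** Against the same subjects' own day-113 values, yes, given a falling curve. Against leaving the samples out, no. Suppose the typical half-life is 21 days and starting levels are equal. A leaver sampled on day 85 then falls below the typical day-113 level if their half-life is under 21 × 85/113 = 15.8 days. For day 71 the threshold is 21 × 71/113 = 13.2 days.

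A simulation used 120 completers, ET days 58 to 85, typical half-lives of 14, 21 and 28 days, and assumed CVs of about 30% for level and 25% for half-life. Adding moved samples lowered the mean in about 9 to 11% of runs with one sample, 0.4 to 1% with three, and about 0.1% or less with five or more.

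**6. Visit 5.** An ET sample from a subject with no Visit 5 sample fills Visit 5 from any day between 2 and 85. At 20% dropout and h = 28, 18 subjects leave before day 57, with mean ratio 1.76 to their own day-57 level and 132 subjects sampled at Visit 5. With 4.5, 9 or 18 ET samples the Visit 5 mean is 2%, 5% or 9% high. Restricting to days 29 to 57 (3, 6 or 12 samples, ratio 1.44) cuts this to 1%, 2% or 4%.

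**The case against.** **Rule 4 may have been meant to cover ET.** The lead-in to the rules names both visit types. But a 4-week cap on ET would leave rule 1 almost nothing to do: every parameter with two post-baseline windows uses days 2 to 85 and day 86 onward, so only an ET visit on day 85 could move. If the cap was intended, the text still needs correcting. The comparison with unscheduled visits is also imperfect, because no rule moves those forward from a filled window. That criticism stands, but it does not bring the moved sample any closer to day 113.

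**Treating ET as end of study is the plan's convention.** Table 1 has one EOS/ET column, and the SPT, PFASQ and ADA windows place any post-dose value at Visit 7. This is true. For a concentration that falls steadily after one dose, however, time since dose largely determines the value. It is also true that SAP 6.4's opening sentence does not list PK among by-visit data, although the window table does.

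**Other outputs reduce the harm.** Actual time is kept, Protocol 11.4.7 looks at individual PK profiles for ADA influence, and the median and quartiles move less than the mean. These help, but they do not correct the visit means or the nominal-time plot, and Protocol 11.4.7 does not specify the time axis.

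**The size rests on stacked assumptions.** This stands in full. Half-life, dropout timing and ET attendance are undocumented, and the top of each range needs every post-Visit-5 leaver to return.

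**Stronger readings.** A reader might infer that the rule can only raise the Visit 7 mean. Step 5 shows otherwise: a fast-clearing or ADA-affected leaver can lower it relative to omitting the sample. A reader might also infer that the case for the 900 mg dose is compromised. The 10 mg/L statement in Protocol 3.2.2 describes the earlier study, and neither document compares this trial's Visit 7 mean with it.

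**Conclusion.** The point holds as a minor correction. Followed as written, SAP 6.4 reports some PK samples at day 113 that were drawn at least 28 days earlier, and the stated distance limit does not stop it. Each such sample overstates its own subject's day-113 level, by about 2.0 to 2.5 times at day 85 under assumed half-lives of 28 to 21 days.

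The Visit 7 mean is likely, not certain, to be higher than if the samples were omitted. The illustrative range is 1 to 7% at 5% dropout and 5 to 29% at the 20% allowance, and it depends on half-life, dropout timing and ET attendance that the documents do not give. The displacement of 28 days or more needs no assumption.

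PK is descriptive, with no hypothesis test (Protocol 11.4.6.1). No primary result, test or type I error is affected, and no stated decision depends on this mean.

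**What to change.** Add to SAP 6.4:

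> Rule 1 does not apply to PK. An early-termination PK sample is used for a visit only if that visit has no scheduled sample, the sample falls in that visit's own window, and it is within 4 weeks of the target day (Visit 5: days 29 to 85; Visit 7: days 86 to 141). Other early-termination PK samples are listed and not included in visit means.

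Add to SAP 5.8, keeping the nominal-time mean plot:

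> Individual concentrations will be plotted against actual days since dose.

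The day limits follow from 57 ± 28 and 113 ± 28, cut at the existing boundary between days 85 and 86. Extending rule 4 to ET visits would be shorter and would remove all moves to Visit 7 except from day 85, but it would also change the mapping of laboratory, IgE and PGI-S data, which use the same windows.

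The cost is one mapping rule and one sentence, with no new data. The downside is that the Visit 7 mean rests on slightly fewer subjects and does not describe early dropouts. Their samples remain in the listing and in the actual-time plot.
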